5.2. Statistical analysis

The primary analysis will estimate the mean difference with a 95% confidence interval (CI) in RMDQ score at three months follow-up between groups (selfBACK in addition to usual care versus usual care only). The analyses will be conducted according to the intention-to-treat principle using a linear mixed model for repeated measures. This model includes all available data for all participants at each time point (i.e. baseline, six weeks, and three months). In the regression model, individual participants will be specified as a random effect, accounting for the within subject covariance structure. The effect of group and time will be specified as fixed effects using a joint variable of intervention and time. Here, baseline levels are pooled over the two study groups assuming that any baseline differences are due to chance [73]; this also controls for any baseline differences in the outcome variable. The analysis will investigate the effect of the intervention as constant over time, as well as an interaction between time and group allocation. The between group difference will be estimated both in a crude model, and adjusted for the two variables used for stratification in the randomisation i.e. country and care provider [74]. Further adjustment for baseline levels of other prognostic factors will be considered.

Any missing values are inherently accounted for in the mixed model approach [75], but multiple imputation methods and complete case analysis will be applied in sensitivity analyses. Possible modifiers of the effect of intervention on the primary outcome will be assessed in supplementary analyses stratified by gender, age groups, socioeconomic status and different levels of LBP severity etc., and accompanied by tests of statistical interaction.

Secondary outcomes will be analysed using a similar approach as described above for the primary outcome, with linear mixed models for repeated measures. Analyses of data from six- and nine-months follow-up will also be analysed according to the above description for the primary outcome. The precision of the estimates from the statistical analyses will be assessed by 95% CI.

To increase the transparency, a statistical analysis plan will be agreed upon and made publicly available before the inclusion of participants is completed. Also, to reduce the risk of biased interpretation of results the following procedure will be undertaken: Two interpretations will be drafted based on a review of the primary outcome data with groups arbitrarily labelled as A and B [76]. One interpretation assumes that A is the selfBACK DSS in addition to usual care and B is usual care, the other interpretation assumes that A is the usual care and B is the selfBACK DSS in addition to usual care. After agreeing on both interpretations, the randomisation code is then broken and the correct interpretation will be chosen.

6. Data collection

The outlined data collection and data management is valid for the RCT and process evaluation (see section 8).

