2.3. Selection criteria

Participants must meet all the following eligibility criteria:

- Seeking care from primary health-care practice or a specialised outpatient hospital facility (DK) for non-specific LBP within the past 8 weeks
- LBP of any duration
- Mild-to severe pain-related disability rated as 6 or above on the Roland Morris Disability Questionnaire (RMDQ)
- Age ≥ 18 years
- Own and regularly use a smart phone (with at least Android 6.0+ or iOS11.0+) with internet access (Wi-Fi and/or mobile data)
- Have a working email address and have access to a computer with internet access to complete questionnaires in a web browser.

Presence of any of the following criteria will exclude participants from enrolling in the RCT:

- Not interested
- Unable to speak, read or write in the national language (Danish/ Norwegian)
- Cognitive impairment or learning disabilities
- Mental or physical disease or health problem limiting participation in the study (Examples are fractures or pathologies, such as cancer, inflammatory diseases, and signs of radiculopathy (severe leg pain, loss of leg strength, or loss of or altered sensation in a myotomal or dermatomal distribution))
- Unable to take part in exercise/physical activity (such as non-ambulatory patients, use of walking aids/assistance, unable to get down and up from the floor independently)
- Fibromyalgia (diagnosed by a health care professional (HCP))

- Pregnancy
- Previous back surgery
- Ongoing participation in other research trials for LBP management.

The assessment of whether the criteria are considered to limit participation is performed either by the referring HCP during the recruitment phase (see green box in **Figure 1**) or by participant self-report during the screening call (see blue box in **Figure 1**).

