2.5. Screening for eligibility and enrolment by researchers

The screening process is outlined in the blue box in **Figure 1**. Participants who have indicated that they are interested in the project are contacted via telephone by a researcher in the selfBACK team. During this call, oral information about the trial is given to the participant and questions about the project and project participation can be answered. A detailed eligibility screening is performed via a pre-defined screening form including the inclusion and exclusion criteria described above.

The enrolment process is outlined in the grey box in **Figure 1**. If eligible and willing to participate, the participants give their verbal consent to participate and are sent an email with a link to the web-based baseline questionnaire. After a participant has completed the baseline questionnaire the informed consent will be signed, and the randomisation performed via a web-based randomisation system (see section 2.6). A small difference in this procedure is evident between countries due to

difference in requirements from the local Ethics Committees. In NO, the written consent form is included in the written information provided by the HCP. The participant can return the signed informed consent in a pre-stamped envelope as provided by the HCP or alternatively, the participant can take a picture of the signed consent form and send it via a text message to the researchers. Hereafter, the researcher will call the participant and inform about the result of the randomisation and give instructions according to group allocation. If randomised to the control group, all instructions are completed on the phone. If randomised to the intervention group, the participant is required to attend a face-to-face meeting to have the app installed on their phone and be given the wristband to wear. In DK, all participants are invited to a face-to-face meeting, where the consent form is signed and hereafter the randomisation is performed. All instructions are given verbally at this meeting.

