4.1. Primary outcome

The RMDQ assesses pain-related disability [43]. The questionnaire includes 24 items asking participants to indicate if they experience functional impairments by answering “yes” or “no” to a series of descriptions of functional abilities [44]. The RMDQ score ranges from 0 to 24, where a higher score indicates higher levels of disability due to LBP [44, 45]. The RMDQ is a validated and recommended tool for measuring pain-related disability in LBP populations [41, 45, 46]. The minimal clinically important difference for the RMDQ has been reported to be five points in LBP populations with baseline scores ranging between 14-16 points [47]. The selfBACK trial aims to detect a two-point difference after three months. This is less than the suggested five-point reduction stated as minimally clinically important. Also, if the two-point difference does not exceed the measurement error of the RMDQ, the results will then be difficult to apply on an individual level in clinical practice. The measurement error of the RMDQ has been reported to range between 1.4-3.7 in studies comparing the RMDQ to the Oswestry Disability Index, with three studies reporting measurement error to range between 1.4 to 1.8 and one study reporting 3.7 [48]. Given that the selfBACK intervention is an add-on to usual care and supposed to be a supplement to existing treatment rather than a substitution, a smaller difference can be justified.

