5.1. Sample size estimations

The study is designed as a superiority trial with two parallel groups, selfBACK in addition to usual care versus usual care only. We hypothesis that the intervention group (selfBACK in addition to usual care) will have a two-point difference in pain related disability (RMDQ) compared to the control group (usual care) at three months follow-up. The sample size calculations have been performed in two ways. First, we conducted a simple calculation assuming only one follow-up measure and a standard deviation (SD) of the RMDQ score of six points. The expected SD was informed by previous high-quality studies in DK and UK investigating similar LBP populations [67-70]. Based on these calculations we estimated that a sample size of 382 (191 in each group) was necessary to detect a two-point difference with 90% power and a two-sided alpha level of 0.05.

We then performed a simulation using 1000 repetitions of a mixed model regression for repeated measures, assuming 1) three data points per participant (i.e. baseline, six weeks and, three months), 2) an effect of treatment of two points, 3) a SD of six points, and 4) a correlation between repeated measures of 0.4. The latter was based on information from previous trials with repeated measures for the RMDQ in similar LBP populations [71, 72]. As in the simple calculations reported above, we used an alpha level of 0.05. Based on these assumptions, sample size calculations showed that 250 participants (i.e. 125 participants in each group) give a power of 92% (95% confidence interval [CI 90-93]) to detect a two-point difference in RMDQ between study groups at three months. Furthermore, simulations assuming a two-point difference between groups at both six weeks and three months indicated that a sample size of 180 (90 in each group) give a power of 94% (95% CI, 92-95). Taken together, these sample size calculations indicate that a sample size of ~250 persons (125 in each group) will be sufficient under the given assumptions if the statistical analyses utilise the repeated measure design. A recent systematic review showed that attrition rates ranged between 4-94% for digital self-management interventions lasting between two weeks and 12 months in LBP populations [25]. To allow for a 30%

drop out rate at three months follow-up we aim at including a total of 350 participants in the trial; 175 participants in each arm.

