#### Effectiveness measures

Effectiveness measures applied in the cost-effectiveness analyses correspond to the clinical endpoints in the trial. These statistical analyses are described in the clinical trial protocol.

For the EQ-5D-5L index values, central tendency and dispersion measures will be presented for both groups at baseline, 6 weeks, 3, 6, and 9 months after the inclusion in the trial. These

will be presented along with median values and the 25th and the 75th percentiles, as recommended by the EuroQoL Group.

Multivariable regression analyses will be used to estimate incremental QALYs. Because QALYs are normally left-skewed, general linear models are considered. Two models are estimated; a base-case model, adjusting for baseline utility values, and a model that, in addition, includes the variables adjusted for in the main trial. The base-case model is estimated both using missing values being imputed and using complete cases.

Baseline characteristics will be reported as percentages for binary variables and mean values and SDs for continuous variables.

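### Protocol 5.2 names only a participant random effect for the within-person covariance; stating an unstructured covariance or robust standard errors would guard the primary SE against a modest error of either sign

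*Protocol*

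**What the plan says.** Protocol 5.2 describes an intention-to-treat linear mixed model in which baseline, six weeks and three months are all outcome rows. Baseline is pooled across arms, and group and time enter through a joint fixed effect. On covariance it says that "individual participants will be specified as a random effect, accounting for the within subject covariance structure". It names no visit-specific variance, no residual structure and no robust standard error.

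The same model is carried forward: "Analyses of data from six- and nine-months follow-up will also be analysed according to the above description for the primary outcome". Secondary outcomes get a similar approach.

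The simulation in Protocol 5.1 uses a single SD and a single correlation: "a SD of six points, and 4) a correlation between repeated measures of 0.4".

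Two design features bear on the variances. Protocol 2.3 requires an RMDQ of at least 6, and the SAP (Settings and Participants) places that score at screening. By Protocol 2.5, those found eligible in the screening call then "are sent an email with a link to the web-based baseline questionnaire", so baseline is a separate, later measurement. Protocol 4.1 adds that "The RMDQ score ranges from 0 to 24".

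The supplied SAP covers cost-effectiveness. For the clinical effectiveness measures it says only: "These statistical analyses are described in the clinical trial protocol". Protocol 5.2 also promises that "a statistical analysis plan will be agreed upon and made publicly available before the inclusion of participants is completed". SAP Section 1 says that the main trial's SAP was published as a supplement; it is not among the documents reviewed.

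**The concern.** A participant random effect with ordinary residuals implies one variance at all visits and one correlation for all pairs. The model-based SE of the three-month difference is right only if that pattern holds, at least approximately.

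The design gives reasons to doubt it in both directions. Selection on a correlated screening score narrows the spread at baseline more than at follow-up, which makes the SE too small. If patients improve, scores pile up near zero and follow-up spread can fall below baseline spread, which makes the SE too large. The quantities at stake are the primary 95% confidence interval and p-value, and then the later visits and secondary outcomes analysed in the same way.

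**Working it through.** **The plan's own inputs.** SD 6 and correlation 0.4 at all visits come from Protocol 5.1. The simple calculation there (SD 6, two points, 90% power, two-sided 0.05) reproduces: about 190 per arm against the stated 191. The stated 92% power with 250 participants does not reproduce for the three-month contrast. The variance below gives SE √(2/125 × 30.24) = 0.696 and power Φ(2/0.696 − 1.96), about 82%. That is a separate matter; the error rates below do not depend on it.

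**Closed form, complete data, equal arms.** Let V0 and V3 be the baseline and three-month variances, and C03 their covariance.

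- Random-intercept estimate: d3 − ρ·d0, where d3 and d0 are the arm differences and ρ = mean covariance / mean variance over the three visits.
- Variance the model reports: proportional to s²(1 − ρ²), with s² the mean of the three variances.
- True variance: proportional to V3 + ρ²V0 − 2ρC03.
- Actual two-sided error: 2[1 − Φ(1.96 × model SE / true SE)].

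**At the protocol inputs.** s² = 36 and ρ = 14.4/36 = 0.4. Model: 36 × 0.84 = 30.24. True: 36 + 0.16 × 36 − 0.8 × 14.4 = 30.24. The ratio is 1, so the test is exact.

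**Changing only the baseline SD** (follow-up SD 6, all correlations 0.4; the altered SDs are assumptions):

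| Baseline SD | ρ | Model | True | SE ratio | Error |
|---|---|---|---|---|---|
| 6.0 | 0.400 | 30.24 | 30.24 | 1.000 | 5.00% |
| 5.5 | 0.399 | 28.66 | 30.28 | 0.973 | 5.66% |
| 5.0 | 0.396 | 27.27 | 30.42 | 0.947 | 6.35% |
| 7.0 | 0.397 | 33.99 | 30.38 | 1.058 | 3.82% |

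**Modelling the screening step.** All of the following is assumed: latent normal scores with SD 6 and correlation 0.4, latent mean 8, 10, 12 or 14, screening-baseline correlation 0.5 to 0.9 in steps of 0.1, improvement 0, 2, 3.5 or 5 points, selection at 6 or above on the screening score, and scores rounded and clipped to 0-24. Over the 80 combinations:

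- Error about 3.9% to 6.6%, median about 5.4%; 73 of 80 fall below 6%.
- Model SE over true SE: 0.94 to 1.05.
- Baseline less variable than three months in 63 of 80: 5.1-6.6%. In the other 17: 3.9-5.0%.
- Latent mean 14, which gives a screened baseline mean of about 14-15: 5.1-5.9%. Protocol 4.1 cites baseline scores of 14-16 in other populations, the only RMDQ level in the documents.
- The 6.6% extreme needs latent mean 8, screening-baseline correlation 0.9 and no improvement. The 3.9% extreme needs latent mean 8, correlation 0.5 and a 5-point improvement.

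**Simulation with missing data.** 350 participants, REML, RMDQ missing at random at the SAP Table 3 rates (63/300 at six weeks, 41/300 at three months), 40,000 runs per case, Monte Carlo error about 0.2-0.3 points. Correlation 0.4 throughout:

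| Case | Random intercept | Unstructured | Random intercept, robust SE |
|---|---|---|---|
| Protocol inputs | 5.0% | 5.1% | 4.9% |
| Mean 8, screening r 0.9, improvement 0 | 6.8% | 5.1% | 4.9% |
| Mean 12, screening r 0.8, improvement 3.5 | 5.6% | 5.1% | 4.9% |
| Mean 8, screening r 0.5, improvement 5 | 3.9% | 5.2% | 5.1% |

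The mean estimate was within 0.004 of zero in every case.

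**Practical size.** At SD 6, correlation 0.4 and 175 per arm with complete data, the 95% half-width is 1.96 × √(2/175 × 30.24) = 1.15 points. A 6% error in the SE moves it by about 0.07 points, against a two-point target.

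**The case against.** The best defence is that the equal-variance assumption is nowhere written. The text says that the random effect accounts for the covariance structure; it does not state compound symmetry. The document that would normally settle it, the main-trial SAP, is not available, and silence in a cost-effectiveness SAP proves nothing. Planning used one SD and one correlation, and at those values the model is exact. A random intercept is also a common and legitimate choice. All of this stands, and it keeps the point at low severity.

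A reader might go further in three ways that the documents do not support:

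- **That the primary interval and p-value are known to be wrong or too optimistic.** No visit-specific SDs or correlations are given, the sign of the error is unknown, and quoting only 5.1-6.6% leaves out the conservative cases.
- **That the error reaches 7% or more.** Closed-form values up to 7.5% appear if the two follow-ups are also assumed to correlate 0.6, but Protocol 5.1 gives 0.4. Values up to 7.7% appear if the screening score is treated as the baseline itself, but the documents describe two separate measurements.
- **That the choice of structure cannot touch the estimate.** With complete data both models are unbiased, but realised values can differ. In the most extreme grid case the weight on the baseline difference is 0.30 under the random intercept and 0.35 under the unstructured model, so a one-point chance imbalance shifts the estimate by 0.05 points.

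What the defence does not answer is that the protocol leaves a choice open on its primary result when a safer choice costs almost nothing.

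**Conclusion.** The point holds as a low-severity improvement, not as a demonstrated error. If the model is a random intercept, the primary SE depends on equal variances and equal correlations, which the entry rule and the scale bounds make doubtful. With correlation 0.4, the assumed screening scenarios put the true error of a nominal 5% test at about 3.9-6.6% (median about 5.4%), and at 5.1-5.9% for a screened baseline mean of about 14-15. The SE is off by roughly 6% at most, in either direction. The conclusion rests on the random-intercept reading, on latent normal scores and on invented screening parameters, so the ranges illustrate the size and do not bound it. The effect at six and nine months and on secondary outcomes was not calculated.

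**What to change.** In Protocol 5.2, state that the primary model uses an unstructured covariance over baseline, six weeks and three months, or robust standard errors. Keep the pooled baseline and the group-by-time terms. Apply the same to the six- and nine-month analyses and to continuous secondary outcomes. If the main-trial SAP already names such a structure, simply align the protocol text to it.

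The cost is one sentence and one software option. Three visits need 3 × 4 / 2 = 6 covariance parameters instead of 2, so four more. In the simulations true precision was unchanged: the empirical SD was 0.997-1.001 of that under the random intercept. The reported SE moved only where it had been wrong. It rose 2.6-8.7% where it had been too small (this range includes cases with follow-up correlation 0.6) and fell 3.0-5.7% where it had been too large.

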2.6. Randomisation

Participants are randomised to either a) selfBACK DSS in addition to usual care or b) usual care only. The randomisation is performed as a block randomisation with permuted blocks of random size unknown to the research team and stratified by country and care provider (i.e. general practitioner, physiotherapist,

chiropractor, or Spine Centre). The allocation ratio between the SELFBACK DSS in addition to usual care and the usual care groups is 1:1. Randomisation will be performed by a web-based randomisation system (Web Case Report Form; WebCRF) developed and administered by Unit of Applied Clinical Research, Faculty of Medicine and Health Sciences, NTNU, Trondheim, Norway. This unit is not otherwise involved in the trial management or trial conduct. A contractual agreement has been signed with the Unit of Applied Clinical Research concerning their role and responsibilities in the project. The WebCRF system will hold a minimal data set on all screened participants (variables include: a trial id number, country, care provider, recruitment site, age, gender).

2.7. *Blinding*

The study is a single-blinded study. Participants are not blinded to group allocation. The analysis and interpretation of the study results will be performed by researchers blinded to group allocation. Once the study is completed, a copy of the data will be extracted in pseudonymised form for statistical analyses. All personal information that may lead back to specific participants (i.e. e-mail address, username etc.) will be removed from the data. The information concerning group allocation will be added to the dataset with the intervention and control group randomly labelled as A and B. The randomisation key (i.e. document entailing information on which group is which) is kept at the Unit of Applied Clinical Research at NTNU. They will provide the randomisation key to the research team once a blinded interpretation of the results is finalized (see section 5.2).

3. Interventions

3.1. *Usual care*

Participants randomised to usual care will follow any diagnostic or treatment-related pathway (e.g. receive information, advice or treatment) as instructed by their HCP. They are also allowed to seek care, treatment or help elsewhere as normal. After the completion of the trial at 9 months, participants who have completed all follow-up assessments are contacted and offered a wearable device similar to the SELFBACK intervention group.

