3.2.4. Access, frequency and mode of delivery

The participants access their self-management plan via the selfBACK app and enter data into the DSS by answering tailoring questions in the app and by wearing the connected wearable device. These data are combined with the participant self-reported outcome as outlined in Figure 2. The participant is encouraged to use the selfBACK app daily or at least once a week, in order to be offered a new self-management plan. The app will send push-notifications reminding the participant to open the app and view the new self-management plan. The participant can disable or adjust the frequency of notifications in the app settings. The goal of the intervention is that participants learn to self-manage their LBP, which may potentially result in participants discontinuing their use of the app. Consequently, discontinuation is not necessarily a sign of low compliance but may indicate a high self-management level.

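### No planned analysis of three-month RMDQ in the supplied documents departs from missing at random, so agreement between them cannot show robustness to outcome-related non-response

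*Protocol*

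**What the plan says.** Protocol section 5.2 makes a linear mixed model on baseline, six-week and three-month RMDQ the primary analysis. On missing data it states: "Any missing values are inherently accounted for in the mixed model approach". It then says that "multiple imputation methods and complete case analysis will be applied in sensitivity analyses". It names no missing-data assumption, does not describe the imputation model, and plans no delta-adjusted, pattern-mixture, reference-based or tipping-point analysis.

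Three other places bear on the point:

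- Section 2.7 says: "Participants are not blinded to group allocation". The RMDQ is self-reported (section 4.1).
- Section 5.1 allows for 30% drop-out at three months and cites attrition of 4-94% in digital self-management interventions for low back pain.
- Section 6.1 plans two reminder e-mails, then a text or telephone contact asking for the RMDQ alone.

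The SAP supplied covers cost-effectiveness only. Its effectiveness section refers back to the protocol for the clinical endpoints. Its missing-data section plans fully conditional multiple imputation from the outcomes at all time points and group allocation, and its cost and QALY models are also fitted to complete cases. Both are of the same kind as the protocol's checks.

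**The concern.** A sensitivity analysis is informative when it relaxes the assumption that is in doubt. A likelihood-based mixed model is valid if missingness depends only on what was observed. Standard multiple imputation from the same variables assumes the same and should give nearly the same answer. Complete case discards the six-week scores of participants without a three-month score, so it needs a stronger assumption. If non-response depends on the unseen three-month score, all three analyses can be wrong together and still agree.

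Participants know their allocation and report their own disability, so non-response could differ between arms in ways related to outcome. The reported agreement of three methods could then be read as evidence of robustness that it does not provide.

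**Working it through.** **Inputs.** Target: "The selfBACK trial aims to detect a two-point difference after three months" (section 4.1). Spread: "a standard deviation (SD) of the RMDQ score of six points" (section 5.1). Correlation of repeated measures 0.4, drop-out 30%, 175 per arm (section 5.1). Missing RMDQ in the Danish cohort, arms pooled (SAP Table 3): 63/300 = 21.0% at six weeks and 41/300 = 13.7% at three months.

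**The plan's own figures.** The simple calculation states that "a sample size of 382 (191 in each group) was necessary to detect a two-point difference with 90% power and a two-sided alpha level"; the level is 0.05. Check: 2 × (1.960 + 1.282)² × 6² / 2² = 189.1, so 190 per arm or 380 in total, against 382. For the drop-out allowance, 350 × 0.70 = 245, close to the roughly 250 evaluable participants required. Both reproduce.

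**Do the planned checks react to outcome-related non-response?** 400 trials of 175 per arm were simulated. Each was analysed by mixed model, multiple imputation under missing at random by arm (20 imputations) and complete-case ANCOVA. In the one-arm scenario, the log-odds of a missing three-month score rise by 1 per 6 RMDQ points in the intervention arm only, with equal missing rates by arm. That mechanism is an assumption, not a document figure. Negative values favour the app; the true effect is 0.

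| Missing | Mixed model | Multiple imputation | Complete case | False-positive rate |
|---|---|---|---|---|
| 30% | -1.22 | -1.25 | -1.29 | 41%, 41%, 46% |
| 13.7% | -0.58 | -0.59 | -0.62 | 15%, 15%, 17% |

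Across the one-arm settings (true effect 0 or 2), the methods differ by at most 0.08 points while each is biased by about 0.6 to 1.3. When scores were missing completely at random, or at random given the six-week score, all three were within 0.06 of the truth, with 4-7% rejection under no effect. Close agreement therefore occurs whether or not the assumption holds.

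**How large must a departure be?** Let E be the benefit estimated under missing at random, p the missing share in an arm, and d the amount by which that arm's missing participants are worse than predicted (I = intervention, C = control). Then

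adjusted benefit = E - (p_I × d_I - p_C × d_C).

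Take E = 2.0, equal p in both arms, and a baseline-adjusted standard error held fixed across shifts:

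SE = √[2 × 6² × (1 - 0.4²) / n] = √(60.48 / n), with n the observed number per arm.

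| Missing | n per arm | SE | 95% CI | One-arm shift that loses significance | Opposite shifts | One-arm shift to zero effect |
|---|---|---|---|---|---|---|
| 30% | 122.5 | 0.70 | 0.62 to 3.38 | 0.623/0.30 = 2.1 | 0.623/0.60 = 1.0 | 2/0.30 = 6.7 |
| 13.7% | 151.0 | 0.63 | 0.76 to 3.24 | 0.760/0.137 = 5.5 | 0.760/0.274 = 2.8 | 2/0.137 = 14.6 |

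If both arms shift equally and p is equal, the term in brackets is zero, so that combination is uninformative.

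**Sensitivity to E and sample size.** Each 0.1-point reduction in E lowers the one-arm tipping point by 0.1/0.30 = 0.33 points at 30% missing and 0.1/0.137 = 0.73 points at 13.7%. The SAP reports 461 randomised. With 230.5 per arm, 13.7% missing and E = 2.0, n = 198.9, SE = 0.55, and the one-arm tipping point rises to (2 - 1.96 × 0.551)/0.137 = 6.7 points.

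**The case against.** **Much of the risk may already be dealt with.** Telephone collection targets the primary outcome. In SAP Table 3 the RMDQ has fewer missing values at three months (41) than the EQ-5D or PSEQ (47 each), which fits that procedure. Missing RMDQ falls from 63 at six weeks to 41 at three months, so at least 22 participants missing at six weeks answered later. Part of the missingness is thus intermittent non-response rather than drop-out. At 13.7%, a one-arm tipping shift of 5.5 points is close to the planning SD of 6, which would be reassuring. All of this stands and bears on the size. None of it tests the mechanism, and the planned analyses would not produce the reassuring figure either.

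**The documents are incomplete.** Protocol section 5.2 promises a main-trial SAP, and the cost-effectiveness SAP says it was published as a supplement. It was not supplied and may say more. The imputation model is unspecified; auxiliary variables could make missing at random more plausible, though they would not test departures from it. This stands, and the point is limited accordingly.

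**Section 3.2.4 does not supply evidence of outcome-related loss.** A reader might infer it from the remark that "discontinuation is not necessarily a sign of low compliance but may indicate a high self-management level". That sentence concerns stopping use of the app, whereas the RMDQ is collected through a separate website and by telephone. It also suggests that some who stop are doing well, the opposite of a worse-than-predicted shift. It should not be cited as evidence about missing outcomes.

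**The trial is complete and its main results are published.** A new analysis of the primary endpoint would be post hoc. This stands, and it limits the point to an improvement.

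**Conclusion.** The point holds in a limited form. No analysis planned in the supplied documents departs from missing at random for three-month RMDQ, and agreement among the three planned methods cannot show how robust the result is to outcome-related non-response.

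The practical weight depends on the missing share: fragile at the planned 30% (about 2.1 points in one arm), much less so at the Danish 13.7% (about 5.5 points in one arm, or 2.8 in opposite directions). These figures assume a 2.0-point estimate, 175 per arm, SD 6, correlation 0.4, equal missingness by arm and a fixed standard error. Missingness by arm and for Norway is not given.

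A reader might go further and infer that the trial's result is biased. The documents give no evidence of that, and the simulated false-positive rates follow from an assumed mechanism. Nor can any analysis establish whether unseen outcomes drive the result; a delta analysis shows only how strong the departure would need to be. Classification: cheap improvement.

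**What to change.** In Protocol section 5.2, replace the plain multiple-imputation check with delta-adjusted multiple imputation of three-month RMDQ:

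- State that the primary mixed model assumes missing at random, and specify the imputation model.
- Include delta = 0 as the missing-at-random reference.
- Shift imputed values separately in each arm, in both directions, and include opposite-direction combinations.
- Use the observed missing share in each arm.
- Make the range wide enough to reach the tipping point, or show that it exceeds plausible values. On the assumptions above, a range ending below about 5.5 points would miss the one-arm tipping point at 13.7% missing.
- Report the shifts at which the conclusion changes, and keep complete case as descriptive.

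If the main-trial SAP already contains such an analysis, a cross-reference is enough. For the published primary endpoint, label the analysis post hoc. The same step can be added to the cost-effectiveness imputation, where 66/300 = 22.0% of RMDQ values are missing at nine months.

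Cost: a few hours, because the shift is added to values already being imputed, and one more table.
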